### **5.2.2 Secondary Outcome Variables (if applicable)**

E-Cigarette Craving: The Yale Craving Scale

Salivary Nicotine/Cotinine Levels

### **5.2.3 Exploratory Outcome Variables (if applicable)**

E-cig Appeal: E-cigarette Evaluation Questionnaire (exploratory)

Examine impact of sex, combustible tobacco use and nicotine dependence on experiences from WS-3, WS-23, menthol and nicotine.

Comparative difference among exclusive e-cigarette users of different flavor groups (menthol or mint, fruit /sweet, tobacco), between oral microbiome constitution and inflammatory markers and self-reported oral health.

## **5.3 Study Population**

Participants will be females and male adult e-cigarette users aged 18 years or older.

### **5.3.1 Number of Participants**

We aim to recruit 30 adults for the pilot study and 66 adults for the main study (33 with current cigarette use, 16 reporting menthol cigarette use). In the main study, we will recruit a subset of eligible exclusive e-cigarette users (up to 33) for oral microbiome and inflammation assessment.

### **5.3.2 Eligibility Criteria/Vulnerable Populations**

**For the pilot study:**

**Inclusion Criteria:**

- 18 years or older
- Able to read and write
- Use e-cigarettes containing nicotine
- Have used e-cigs at least 30% of days/past month (at least 8 days on 28-day timeline followback)
- No strong dislike of the menthol flavor
- At least 50% have used only e-cigs with no combustible tobacco products (e.g., cigarettes, cigars, cigarillos) in the past month
- Urine cotinine  $\geq 200\text{ng/ml}$
- Willing to abstain from tobacco/nicotine use 2 hrs prior to sessions
- Not currently quitting/trying to quit nicotine/tobacco use

**Exclusion Criteria:**

- Current criteria for moderate or severe cannabis and alcohol use disorder as per DSM-V criteria
- Current criteria for mild, moderate or severe substance use disorder on any other psychoactive substances as per DSM-V criteria except for tobacco use disorder
- Use of psychoactive drugs including anxiolytics, antidepressants, and other psychostimulants unless prescribed and stable for two months

- Current diagnosis of any severe and untreated psychiatric disorder
- Any significant current medical condition such as neurological, cardiovascular, endocrine, renal, or hepatic pathology that would increase study risk
- Any blood pressure values with systolic <100 or >160 mmHg or diastolic <65 or >100 mmHg
- Allergy to menthol, PG/VG, WS-3, or WS-23
- If of childbearing potential: pregnant, trying to become pregnant or breastfeeding
- Uncontrolled asthma (defined as <20 on Asthma Control Test AND/OR endorsement of “yes” to environmentally induced bronchospasm that requires prescription Epipen
- Medical conditions, including chronic and untreated acute pulmonary conditions, that in the investigators view will increase risk of respiratory problems among participants
- Report of greater than “without any difficulty” on any item of the PROMIS Physical Function Short Form
- For current (past-month use) cannabis vapers: Any report of mild or great EVALI-related symptoms (i.e., cough, shortness of breath, chest pain, nausea, vomiting, stomach pain, diarrhea, fever, chills, or weight loss) without non-EVALI reasonable and proximal cause
- Dislike of menthol flavor

**For the main study:**

**Inclusion Criteria:**

- 18 years or older
- Able to read and write
- Use e-cigarettes containing nicotine
- Have used e-cigs at least 30% of days/past month (at least 8 days on 28-day timeline followback)
- Urine cotinine  $\geq 200\text{ng/ml}$
- Willing to abstain from tobacco/nicotine use 2 hrs prior to sessions
- Not currently quitting/trying to quit nicotine/tobacco use
- *For cigarette using participants only:* use of cigarettes at least 30% of days/past month (at least 8 days on a 28-day timeline followback)
- A subset of eligible participants (exclusive e-cigarette users only) for oral microbiome assessment must be willing to refrain from eating, drinking (except water) or brushing their teeth for 2 hour before saliva collection.

**Exclusion Criteria:**

- Current criteria for moderate or severe cannabis and alcohol use disorder as per DSM-V criteria
- Current criteria for mild, moderate or severe substance use disorder on any other psychoactive substances as per DSM-V criteria except for tobacco use disorder
- Use of psychoactive drugs including anxiolytics, antidepressants, and other psychostimulants unless prescribed and stable for two months

- Current diagnosis of any severe and untreated psychiatric disorder
- Any significant current medical condition such as neurological, cardiovascular, endocrine, renal, or hepatic pathology that would increase study risk
- Any blood pressure values with systolic <100 or >160 mmHg or diastolic <65 or >100 mmHg
- Allergy to menthol, PG/VG, WS-3, or WS-23
- If of childbearing potential: pregnant, trying to become pregnant or breastfeeding
- Uncontrolled asthma (defined as <20 on Asthma Control Test AND/OR endorsement of “yes” to environmentally induced bronchospasm that requires prescription Epipen
- Medical conditions, including chronic and untreated acute pulmonary conditions, that in the investigators view will increase risk of respiratory problems among participants
- Report of greater than “without any difficulty” on any item of the PROMIS Physical Function Short Form
- For current (past-month use) cannabis vapers: Any report of mild or great EVALI-related symptoms (i.e., cough, shortness of breath, chest pain, nausea, vomiting, stomach pain, diarrhea, fever, chills, or weight loss) without non-EVALI reasonable and proximal cause
- For oral microbiome and inflammation assessment, participants who report a medical condition such as diabetes, uncontrolled hypertension, renal and hepatic disorders, antibiotics use in the past 3 months, oral cancer diagnosis, or who are undergoing active treatment for any medical condition

## 6 Methods

### 6.1 Treatment

#### 6.1.1 Identity of Investigational Product

Products used in this study are investigational tobacco products including 16 different e-liquids and 1 e-cigarette device for the pilot study and 18 different e-liquids and 1 e-cigarette device for the main study. The e-cig device to be used will be the Suorin iShare™ pod device. iShare characteristics resemble the popular JUUL device in terms of power output, shape, and size, but with the benefit of refillable cartridges. The Yale TCORS lab core has demonstrated its near 100%-effectiveness in delivering nicotine to users using a custom-made vaping machine. Nicotine concentrations will be 0 mg/ml in the pilot study and will be 59 mg/ml nicotine salt (nicotine benzoate) in the main study, a widely used and well tolerated nicotine salt formulation and concentration, similar in strength to a 5% JUUL product. PG/VG levels for the study e-liquids will be 50:50 PG/VG, a ratio typical of nicotine salt e-liquids and used in previous studies by our group.

E-liquids will be created upon review of the (Investigational Tobacco Product) ITP application by the FDA; [name] leads Yale TCORS ITP applications and will oversee this process. All e-liquids will be created via the Yale Investigational Drug Service (IDS) Pharmacy under the direction and supervision of [name] (Manager, Investigational Drug Service Pharmacy). E-liquid recipes have been developed via the Yale Laboratory Core and with consultation of [name], a chemist with American E-

liquids/Vaping Direct and collaborator in research with our group with years of experience creating e-liquids for research. E-liquid ingredients will be purchased by our group, then shipped to our research team and upon receipt be transported to and stored in the Yale IDS Pharmacy (see 6.1.6) and created in 30mL batches as needed by Yale IDS. A research assistant/associate/fellow will document the receipt from IDS. E-liquid ingredients all meet the requirements of United States Pharmacopeia (USP) or Flavor and Extract Manufacturers Association of the United States (FEMA) "GRAS" (generally recognized as safe) have been reviewed by Yale IDS and the Yale Tobacco Center of Regulatory Science. Additionally, FDA has reviewed the proposed ITP of all e-liquids prior to study start. The e-liquids being created will be produced with three flavors; (1) menthol, (2) WS-3 and 3) WS-23 to create 16 e-liquids for the pilot and 18 e-liquids for the main study. Pilot e-liquids will contain no nicotine and main study e-liquid will contain a fixed amount of nicotine. E-liquid nicotine and flavor profiles will be confirmed and characterized by the Yale TCORS lab core.

### **6.1.2 Dosage, Administration, Schedule**

Regarding the pilot study, participants will receive two puff exposures to each condition; each exposure will be separated by 10 mins to allow the flavor to dissipate. All e-cigarette pods will be filled to 0.5mL of e-liquid.

Regarding the main study, e-cigarette pods will be filled with approximately 0.9mL of e-liquid, which in previous trials has produced at least 30 puffs. Participants will be randomized to receive one of the 3 menthol conditions (no-menthol, low menthol, high menthol, levels determined by the pilot study above) in Lab 1 and will receive the alternative conditions in randomized order in Lab 2 and Lab 3. During each lab session the menthol condition will be paired with three WS-3 concentrations: no WS-3, low (0.1%) WS-3, or high (2.0%) WS-3 or three WS-23 concentrations: low (0.1%) WS-23, high (2.0%) WS-23, or 4% WS-3 (concentration determined by pilot study) in randomized order. All e-cigarettes will contain nicotine salt at a nicotine concentration of ~59mg/ml, commensurate with levels in popular commercially available nicotine salt e-cigarettes. Each exposure will consist of a 5-puff bout (each puff 3-sec long and separated by 30 sec) via a puff topography a device (an apparatus used to measure puffing behavior) and will be separated by 30 mins to allow any sensory effects to dissipate between exposures. The e-cig pods containing e-liquids will be weighed before and after the session.

Participants will be told they can discontinue puffing behavior at any time if they experience discomfort. The lab sessions will be conducted by trained research staff who are sensitive to the population and trained to monitor any potential adverse effects. Heart rate, blood pressure, and pulse oximetry will be assessed at baseline and every in-person visit for safety. If they experience any side effects or concerns during the study, we ask them to let us know. Blood pressure will be taken before and after each e-cigarette exposure during laboratory sessions. A blood pressure and heart monitoring form will be used to assess if blood pressure or heart rate is above or below the following threshold (>180, <100 systolic, >110, <60 diastolic) sessions will be paused and potentially discontinued if blood pressure is unable to return to in range values. If blood pressure is above or below these thresholds, blood pressure will be repeated 2 times to confirm value. Additionally, we will assess blood pressure across

laboratory sessions and contact the study physician if necessary if any concerning trends (with or without threshold blood pressure occur). Participants will be told that they are able to stop the study at any point. If they feel any discomfort or need to stop for any reason, they can let the research team know. In the event of a serious adverse event, the PI ([name]), will consult with Yale Tobacco Center for Regulatory Science (TCORS) co-Is, along with center chemosensory expert [name] to determine if blind needs to be broken. Given all study participants are administered all e-liquids, the study will be paused during this period if this occurs.

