### 4.2 Primary Objective

Examine addiction potential (liking/wanting) and appeal (overall flavor appeal, intensity, sweetness, bitterness, irritation, cooling), following a single exposure (5 puffs) to nicotine-containing e-cigs (~59 mg/ml nicotine salt, commonly used in commercial e-cigs), with one of three WS-3 concentrations (none, low, high) and one of the three WS-23 concentrations (low, high, 4%) in combination with one of three menthol concentrations (none, low, high).

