	Concentration 1	Concentration 2	Concentration 3	Concentration 4	Concentration 5	Concentration 6
WS-3 Block	0.05%	0.1%	0.5%	1.0 %	2.0 %	-
WS-23 Block	0.05%	0.1%	0.5%	1.0 %	2.0 %	4.0%
Menthol Block	0.05%	0.1%	0.5%	1.0 %	2.0 %	-

**Table 2.** Main Study Experimental Design

	No WS-3	Low (0.1%) WS-3 Concentration	High (2.0%) WS-3 Concentration	Low (0.1%) WS-23 Concentration	High (2.0%) WS-23 Concentration	4% WS-23 Concentration
Low (0.1%) Menthol	S 1 -S 66					
High (2.0%) Menthol	S 1 -S 66					
No Menthol	S 1 -S 66					

S=Subject. All subjects (1-66) will be exposed to all conditions in the adjacent table.

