**Main Study:** The purpose of the main study will be to determine sensory responses following exposure to e-liquids containing nicotine and WS-3, WS-23, and menthol. This study will recruit 66 adult e-cigarette users (50% with current cigarette use, of which 50% will use menthol cigarettes), to participate in 3 laboratory sessions, separated by at least 24 hrs. At the intake visit, participation in the oral microbiome and inflammatory marker testing will be optional for exclusive e-cigarette users (up to 33). Specifically, they will be asked to provide saliva and urine samples for oral microbiome and inflammatory marker testing and complete a brief survey about their oral health status. Additionally, participants will be asked to submit their most used e-cigarette device/pods from the past-month for analysis. These will be used as exploratory assessments. During the lab visits, participants will receive all eighteen conditions shown in Table 2 below and will be asked to abstain from tobacco use for two hours prior to session start (to control for time since last tobacco exposure). Participants will be randomized to receive one of the 3 menthol conditions (no-menthol, low menthol, high menthol, levels determined by the pilot study above) in Lab 1 and will receive the alternative conditions in randomized order in Lab 2 and Lab 3. During each lab session the menthol condition will be paired with three WS-3 concentrations: no WS-3, low (0.1%) WS-3, or high (2.0%) WS-3 and three WS-23 concentrations: low (0.1%) WS-23, high (2.0%) WS-23, or 4% WS-23 (concentration determined by pilot study) in randomized order. All e-cigarettes will contain nicotine salt at a nicotine concentration of ~59mg/ml, commensurate with levels in popular commercially available nicotine salt e-cigarettes. Each exposure will consist of a 5-puff bout (each puff 3-sec long and separated by 30 sec.) collected via a puff topography device (an apparatus used to measure puffing behavior) and will be separated by 30 mins to allow any sensory effects to dissipate between exposures. To precisely measure puffing behavior, we will utilize a validated electronic cigarette topography device (eTop). This device connects to a computer with software designed to measure puffing behavior. An e-cigarette is inserted into a silicone mouthpiece and the mouthpiece is connected to tubing which feeds into the device. As a participant inhales this device measure puffing behavior including number of puffs, puff volume, puff duration, puff flow rate (a calculation of volume/time). These indices help us understand vaping behavior and make it possible to compare e-cigarette exposure across participants. Topography mouthpieces are sanitized in between subjects and inhaling e-cigarettes via topography devices present no increased risk to participants. At the end of each of the three lab sessions, participants will choose between the 6 e-liquids they sampled in the lab using a free-choice paradigm (~30 mins).

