
Each session will begin with administration of baseline questionnaires assessing withdrawal and craving, collection of samples to assess nicotine levels, familiarization with the sensory and hedonic rating scales and training in how to puff the lab e-cig. Training will be conducted using e-cigs that contain the base liquid of 50% propylene glycol (PG)/50% vegetable glycerin (VG) with no nicotine. Similar to our earlier trials, after each exposure, participants will rate addiction potential (*liking/wanting*: Drug Effects Questionnaire (DEQ); and appeal (*overall flavor appeal*: Labeled Hedonic Scale (LHS); *flavor intensity*: overall flavor intensity, irritation, coolness, sweetness, bitterness: generalized Labeled Magnitude Scale (gLMS). Salivary nicotine samples will be collected pre-sessions and after each flavor exposure to assess potential impact of nicotine levels on responses, with participants

rinsing their mouths before providing each sample. A brief description of the e-cigarette device and all ingredients that will be used for the pilot and main studies is included in Table 3.

**Table 3.** Description of all investigational tobacco products.

Ingredients or products	Manufacturer name	Concentrations (mg/ml or %)
E-cigarette device	Suorin iShare™	-
PG	JT Baker: Propylene Glycol, U.S.P. - F.C.C.	50%
GL	Fisher Scientific: Glycerol, USP/FCC	50%
Nicotine Salt	Nicotine River: PurNic Smooth Nicotine Salt 100mg/ml in 50PG/50GL	0 or 59mg/ml
Menthol	Sigma-Aldrich: L-Menthol	0.05%, 0.1%, 0.5%, 1.0%, and 2.0%
WS-3	Sigma-Aldrich: WS-3	0.05%, 0.1%, 0.5%, 1.0%, and 2.0%
WS-23	Vigon: 503872	0.05%, 0.1%, 0.5%, 1.0%, 2.0%, and 4.0%

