In the main study session, participants will engage in a 15-min training session of the psychophysical tasks they will use to report sensory experience at Lab 1. For Labs 1-3, participants will engage in six directed puffing bouts (5 puffs/3 sec puffs/30 second interpuff intervals) will be separated by 30 mins to allow any sensory effects to dissipate between exposures, a procedure adapted from [name] previous studies. Puffing will occur using a puff topography device (i.e., an established device in which the e-cigarette is attached to a mouthpiece) to measure the parameters of each puff taken (puff duration, volume, etc.). During the 15-minute training session at Lab 1, participants will familiarize themselves with vaping using a puff topography device. Following bout, participants will complete in the following order measures of overall liking/disliking, intensities of sweetness, bitterness, cooling, and irritation/harshness, and where irritation/harshness is felt (i.e., mouth, throat, both). Sensory measures will be followed by collection of general appeal and reinforcing efficacy measures, and a post-exposure measure of craving (collected 15-min after exposure). Cardiovascular measures, including blood pressure and heart rate, will be recorded both before and after each bout session. Participants will be randomized to receive one of the 3 menthol conditions (no-menthol, low menthol, high menthol, levels determined by the pilot study above) in Lab 1 and will receive the alternative conditions in randomized order in Lab 2 and Lab 3. During each lab session the menthol condition will be paired with three WS-3 concentrations: no WS-3, low WS-3, or high WS-3 and three WS-23 concentrations: low WS-23, high WS-23, or 4% WS-23 (concentration determined by pilot study) in randomized order. E-cig pods containing e-liquids will be weighed before and after the session. Lab sessions will occur no more frequently than every 24-hrs. At the end of

each of the three lab sessions, participants will choose between the 6 e-liquids they sampled in the lab using a free-choice paradigm.

**Debrief:** Following study completion, participants will be thanked for their participation and will be given information from the CDC on cigarette smoking and e-cigarette cessation.

**Table 4.** List of Study Assessments

	Pre-screening	Intake (pilot)	Lab 1 (Pilot)	Intake (main)	Lab 1 (main)	Lab 2 (main)	Lab 3 (main)
Contact Info & Eligibility Review	X						
Informed Consent		X		X			

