### **6.4 Statistical Method**

#### **6.4.1 Statistical Design**

Preliminary analyses will provide an overview of the data (e.g., randomization success, outcome distribution, missingness patterns). Outcome analyses will be intent-to-treat and use mixed-effects models which allow for different numbers of observations/subject, use all available data, and can handle missing-at-random data. If model assumptions will appear to be violated, we will transform the data or fit more flexible generalized linear or nonparametric mixed models. For the pilot study, separate mixed-effects models will examine the influence of different concentrations of menthol, WS-23 and WS-3 on coolness and overall intensity and will be used to select the concentrations of menthol and WS-3 that product the weak but detectable coolness and the maximum coolness. For the main study, separate mixed-effects model will include menthol (0, Concentration 1, Concentration 2), WS-3 (0, Concentration 1, Concentration 2), WS-23 (0, Concentration 1, Concentration 2, Concentration 3) and time within lab as factors, all interactions among those factors and adjust for stratification variables. A combination of random effects and structured variance-covariance matrices will be used to account for within-subject correlations. The best-fitting structure will be selected based on Akaike information criterion (AIC). For the main study, higher liking/wanting for WS-3 (at Concentration 1 or 2) or WS-23 (at Concentration 1 or 2 or 3) combined with menthol (at Concentration 1 or 2), compared to menthol alone, will be supportive of the primary hypothesis. Similar models will examine the other outcomes and interactions of different concentration combinations of WS-3, WS-23 and menthol with nicotine. Exploratory analyses will also consider the impact of sex, combustible tobacco use and nicotine dependence on experiences from WS-3, menthol and nicotine.

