#### **6.4.2 Sample Size Considerations**

For our pilot study, we will recruit 30 subjects. While we did not conduct a power calculation for this pilot study, we conducted a similar pilot study with 10 participants in our earlier work with multiple menthol concentrations, and do not anticipate any problems with identifying differences in coolness between the WS-3 and menthol concentrations. For the main study, we will recruit 66 subjects. With an anticipated dropout of 10%, 60 subjects are expected to have complete data. Because we have 4 primary hypotheses (each WS-3 concentration X each menthol concentration > menthol concentration alone), we used a Bonferroni-corrected alpha=0.1. With N=60 completers and a SD of paired differences of 25 as observed in our prior data, we have 80% power to detect a difference of 11.4 (moderate effect size  $d'=.45$ ) in liking/wanting (0-100 scale) between each WS-3 concentration X each menthol concentration and menthol alone using a paired t-test at alpha=0.01.

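### Does the mention of 4% WS-3 in section 6.1.2 leave the main-study conditions in doubt?

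*Combined protocol and SAP*

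**What the plan says.** Section 6.1.2 pairs the session's menthol level with WS-3 at none, 0.1% or 2.0%, and then gives "three WS-23 concentrations: low (0.1%) WS-23, high (2.0%) WS-23, or 4% WS-3 (concentration determined by pilot study". The WS-3 list and this list are joined by *or*.

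The other places that name the main-study 4% condition are:

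- Section 4.2: "one of the three WS-23 concentrations (low, high, 4" percent.
- Section 5.1, Table 2, column heading: "4% WS-23 Concentration".
- Section 5.1, main-study text: "three WS-23 concentrations: low (0.1%) WS-23, high (2.0%) WS-23, or 4% WS-23 (concentration determined by pilot study", joined to the WS-3 list by *and*.
- Section 6.3: "three WS-23 concentrations: low WS-23, high WS-23, or 4% WS-23 (concentration determined by pilot study", also joined by *and*.

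Three further places bear on the point:

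- Table 3 in section 5.1 gives WS-23 as "0.05%, 0.1%, 0.5%, 1.0%, 2.0%, and 4.0" percent. Its WS-3 and menthol rows stop at 2.0%. Table 1 has a 4.0% entry in the WS-23 block only.
- Sections 6.4.1 and 6.5.1 give the main-study coolant factors as "WS-3 (0, Concentration 1, Concentration 2), WS-23 (0, Concentration 1, Concentration 2, Concentration 3".
- Section 6.4.2 counts "4 primary hypotheses (each WS-3 concentration X each menthol concentration", each compared with menthol alone.

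**The concern.** Section 6.1.2 is where a reader looks for what participants receive. Taken at its last item, it puts a 4% WS-3 liquid into the main study. The pilot did not test such a liquid, although the same phrase says that the pilot determined the concentration. The product table does not list it and the model has no level for it. If the item were acted on, WS-3 would have a third non-zero level, WS-23 would lose its highest one, and the fitted factors would not match the conditions given. Every participant is to receive every condition, so the mismatch would reach the whole sample.

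**Working it through.** No sample-size formula applies. The check compares the sections and counts conditions.

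**1. Places naming the main-study 4% condition.** Section 4.2, Table 2, section 5.1 and section 6.3 say WS-23; section 6.1.2 says WS-3. That is 4 against 1, out of 5.

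**2. Pilot liquids.** Table 1 has 5 WS-3, 6 WS-23 and 5 menthol concentrations: 5 + 6 + 5 = 16, the number in section 6.1.1. None of the 16 is 4% WS-3.

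**3. Main-study total.** Three menthol levels x 6 coolant conditions = 18, the number in section 6.1.1. The total is 18 whichever compound the 4% belongs to, so it cannot show the discrepancy.

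**4. Factor levels.** These can show it.

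| Source | WS-3 levels | WS-23 levels |
|---|---|---|
| Table 2 | 0, 0.1%, 2.0% (3) | 0, 0.1%, 2.0%, 4% (4) |
| Sections 6.4.1 and 6.5.1 | 3 | 4 |
| Section 6.1.2, last item taken literally | 0, 0.1%, 2.0%, 4% (4) | 0, 0.1%, 2.0% (3) |

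The third row follows only if the last item is taken at its word and the phrase introducing the list is ignored. The full sentence promises three WS-23 concentrations, so it does not describe a coherent alternative design.

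**5. Hypothesis count.** Two non-zero WS-3 levels x two non-zero menthol levels = 4, as in section 6.4.2; the literal item would give 3 x 2 = 6. This is weak evidence, because section 6.4.2 leaves WS-23 out of the count and so cannot show where a WS-23 condition belongs.

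**6. The joining word.** If *or* meant one coolant list per session, there would be 3 coolant conditions x 3 sessions = 9, not 18. Section 6.3 specifies six puffing bouts per session and a choice among six liquids, and 6 x 3 = 18. The same sentence therefore holds a second slip of the same kind.

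**7. What depends on the item.** The power statement uses 60 completers, an SD of 25 and a difference of 11.4 points for WS-3 with menthol against menthol alone. None of these inputs refers to a 4% condition. The model is defined by the levels in sections 6.4.1 and 6.5.1, which fit Table 2.

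**8. From text to pod.** Under section 6.1.6 the study biostatisticians generate the condition orders before the study starts, and the person filling pods works from that sheet. Section 6.1.1 adds recipes already developed and FDA review of the proposed products. Sections 6.1.1 and 6.1.5 provide for laboratory confirmation of nicotine and flavor profiles.

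**The case for a change.** The best argument for treating this as more than a slip is that a mistake would be hard to see. Pods are letter-coded and double-blinded (section 6.1.4), and section 2.2 describes the synthetic coolants as odorless and tasteless, so session staff could not readily tell one from another. The total of 18 does not catch the error. If the item were followed, 1 coolant condition x 3 menthol levels = 3 of the 18 conditions would be affected in every participant. The current revision is dated 8/01/25 and main-study recruitment was to follow a pilot expected to finish around the end of 2024, so this may be the text in use.

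It stands that the sections contradict each other and must be reconciled, including *or* against *and*, so that one list of six coolant conditions per session appears throughout. It does not stand that the trial has two competing designs. The 3-of-18 figure requires someone to follow one list item against its own introductory phrase, Table 2, Table 3, and sections 4.2, 5.1 and 6.3, and requires the recipe, product-review and laboratory checks all to miss it. Nothing in the documents suggests that this happened or would happen.

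**Conclusion.** This is a clerical inconsistency with no statistical consequence: one item in one of five places, plus one conjunction in the same sentence. The objectives, design tables, procedures and model describe one set of 18 conditions, and an analyst working from Table 2 and section 6.4.1 would code the factors without difficulty. Correcting the sentence would change neither what the trial does nor what it can conclude, so no change to the design or analysis follows.

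This rests on one assumption that the documents cannot confirm: that the randomisation sheet and pharmacy recipes, which are not reproduced in them, carry the Table 2 list of conditions. The wording still has to be reconciled editorially across sections 4.2, 5.1, 6.1.2 and 6.3, and this review takes no position on which concentration is right.
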